#### Plan for measurement of these outcomes:

- The Primary outcome measures will be:
  - o Change in 7 point pain Visual Analogue Scale (VAS)
- Secondary outcome measures include:
  - Hip Disability and Osteoarthritis Outcome Score (HOOS)
    - Western Ontario and McMaster Universities Arthritis Index (WOMAC), calculated as a subscore of the HOOS
  - Patient Reported Outcome Measurement Information System (PROMIS) Global Health Scale
  - o Serum Biomarker analysis: IFN-g, IL-6, MCP-1, MIP-1b, IL-1b, TNF-alpha, high-sensitivity CRP, COMP
  - Change in Kellgren-Lawrence classification scores calculated from AP pelvis radiographs between pre-treatment and 1 year post-treatment

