## **Methods:**

#### **Inclusion Criteria:**

- Patients with symptomatic FAI with duration of symptoms for at least 6 weeks
- Clinical and radiographic evidence of FAI defined as the presence of a cam, pincer or combined lesion apparent from radiographs
- Mild to moderate osteoarthritis (Kellgren-Lawrence grade  $\leq 2$ )
- Patients able to provide consent to study participation
- VAS pain level of  $\geq 5$

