#### Patient Selection:

[name] and [name] see patients with hip pain as part of their routine clinical practice. They will do all the screening of potential patients. Once a patient has been enrolled in the study, he/she will be rescheduled and that subsequent visit will serve as their initial study visit. During that initial study visit the patient will be randomized to one of the two treatment arms and the injection will be performed.

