## Randomization Technique

Patients who meet the eligibility criteria will be assigned to steroid or PRP treatment using randomly assigned permuted blocks of 5, created with the random number generator function within STATA, to maintain equal group sizes.

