#### **Data Collection:**

Data collection will be collected and entered by orthopedic surgery research team member assigned to the study and stored into a REDCap database via Ipad. This includes clinical data, radiographic data and analysis of serum biomarkers.

Subjects' hip pain levels will be assessed via standardized orthopedic survey tools (7 point pain VAS, Western Ontario and McMaster Universities Arthritis Index (WOMAC), Hip Disability and Osteoarthritis Outcome Score (HOOS), Patient Reported Outcome Measurement Information System (PROMIS) Global Health Scale) at baseline, 6 weeks, 3 month, 6 months, and 12 months.

Hip radiographs will be performed at baseline and at 12 months, and graded Stage 1-4 via Kellgren-Lawrence classification in a blinded fashion by [name] as described.

Biomarkers analysis will be performed in [name] lab as described. Serum will be aliquoted and stored at -80°C in a de-identified fashion in secured freezers in [name] lab.

Samples will be analyzed in duplicate at each time point, and interassay coefficients of variation will be calculated. For hsCRP (Calbiotech) and COMP (R&D Systems), ELISAs will be performed following manufacturer's instructions. For IFN-g, IL-6, MCP-1, MIP-1b, IL-1b and TNF-alpha, a multiplex Luminex-based assay (Millipore) will be performed following manufacturer's instructions.

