#### **Data Analysis:**

The study sample size is based upon power calculations for change in pain score data from a previous study by our group in patients with FAI. To detect a difference in the change in pain between the first and last visit of 1.7 units, on a 7-point pain scale, using a power of 80% and  $\alpha$ =0.05, requires at total N of 32, or 16 per group. To account for 20% of patients who might withdraw, we will recruit 8 additional subjects for a total of 40 patients. We will use a mixed-effects linear regression model to look at the changes in individual parameters at multiple time points over the course of the study, as well as the associations between changes of multiple parameters. Independent variables in the model are treatment assignment and time, dependent

variables are outcomes scores, biomarkers and Kellgren-Lawrence scores. First, we will perform univariate and univariable models to explore the relative importance of each predictor variable followed by a stepwise procedure in which we will include all significant variables in multivariable model followed by dropping the highest non-significant variable (significance will be set at p=0.10) until only significant variables remain. This will be repeated for each dependent variable. The robustness will be tested by performing model fitting and examining residual plots.

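### The VAS analysis neither adjusts for baseline pain nor constrains the arms to a common baseline mean, so part of any chance baseline difference is carried into the result

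*Combined protocol and SAP*

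**What the plan says.** The primary outcome is change in pain on a 7-point VAS (Plan for measurement of these outcomes). The sample size rests on the same quantity: "To detect a difference in the change in pain between the first and last visit of 1.7 units", with 80% power and alpha 0.05, needing 16 per group, or 32 in all, and 40 recruited to allow for 20% withdrawal (Data Analysis).

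The analysis is a linear mixed model. "Independent variables in the model are treatment assignment and time" is the full statement of its terms, and a selection procedure follows that ends by "dropping the highest non-significant variable (significance will be set at p=0.10) until only significant variables remain". The text does not say whether baseline is one of the modelled responses or whether a treatment-by-time term is fitted. Potential Pitfalls and Limitations names a repeated measures ANOVA as the alternative and says nothing about baseline.

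Baseline VAS will be available: pain is assessed "at baseline, 6 weeks, 3 month, 6 months, and 12 months" (Data Collection). Allocation uses "randomly assigned permuted blocks of 5" without stratification on pain (Randomization Technique). Entry requires a "VAS pain level of" at least 5 (Inclusion Criteria), without saying which scale that threshold is on.

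**The concern.** A difference in mean change treats each unit of baseline pain as worth exactly one unit of follow-up pain. If the true slope is below 1, as regression to the mean after selecting patients in pain would suggest, subtraction over-corrects a baseline imbalance. If the slope is above 1, it under-corrects. Modelling change directly, or keeping baseline as a response with a free baseline mean per arm and a treatment-by-time term, gives this same change contrast at 12 months.

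With about 16 completers per arm and no stratification on pain, some imbalance is likely. Two things are at stake. Part of that imbalance moves the primary estimate in the trial as run, and the plan leaves its handling to be settled after the data are seen.

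**Working it through.** **The plan's own figure.** The SD of change is not stated, so the 32 cannot be recomputed independently. Solving a two-sided t-test for 80% power at 16 per arm and a difference of 1.7 gives SD 1.661; the normal approximation gives 1.716. Either is consistent with 16 per arm. The withdrawal allowance checks: 32 / (1 − 0.20) = 40. The SE of the change contrast is 1.661 × √(2/16) = 0.587.

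**Assumed inputs, not in the documents.**
- Baseline SD s0. If the entry threshold is on the 7-point scale, the range is narrow: at most 0.5 if only 5 and 6 are possible (a 0–6 scale), 0.82 if scores spread evenly over 5, 6 and 7, and 1.0 as the most that 5–7 allows (half at 5, half at 7).
- Correlation r of baseline with 12-month VAS: 0.1 to 0.5.
- Two-sided test, true difference 1.7, 16 completers per arm.

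**Formulas.**
- Follow-up SD implied by an SD of change of 1.661: s1 = r·s0 + √[(r·s0)² − s0² + 1.661²].
- Slope of follow-up on baseline: b = r·s1/s0.
- SE of the chance baseline difference: s0 × √(2/16), giving 0.177, 0.290 and 0.354 units at s0 = 0.5, 0.82 and 1.0.
- Shift in the change contrast for a 1-SE imbalance: (b − 1) × that SE.
- Share of the contrast's sampling variance due to imbalance: [(1 − b)·s0 / 1.661]².

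**Middle case, s0 = 0.82 and r = 0.3.** s1 = 0.246 + √(0.0605 − 0.6724 + 2.758) = 1.711. b = 0.3 × 1.711/0.82 = 0.626. Shift = −0.374 × 0.290 = −0.108 units. Share = (0.374 × 0.82/1.661)² = 3%.

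**Results.** Adjusted power is from simulated 12-month analysis of covariance with 29 residual df and 200,000 trials per cell. The change score has 80% throughout.

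| s0 | r | b | 1-SE shift (units) | Variance share | Adjusted power |
|---|---|---|---|---|---|
| 0.5 | 0.1 | 0.33 | −0.119 | 4% | 80.2% |
| 0.5 | 0.3 | 1.04 | +0.008 | 0% | 78.6% |
| 0.5 | 0.5 | 1.85 | +0.151 | 7% | 81.2% |
| 0.82 | 0.1 | 0.19 | −0.236 | 16% | 85.1% |
| 0.82 | 0.3 | 0.63 | −0.108 | 3% | 79.9% |
| 0.82 | 0.5 | 1.16 | +0.048 | 1% | 78.9% |
| 1.0 | 0.1 | 0.14 | −0.303 | 27% | 89.4% |
| 1.0 | 0.3 | 0.50 | −0.178 | 9% | 82.1% |
| 1.0 | 0.5 | 0.96 | −0.015 | 0% | 78.6% |

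The largest shift is 0.303/1.7 = 18% of the target difference. With r = 0.2 and 0.4 included there are 15 cells, and the variance share is 10% or less in 12 of them. The power gain is gone from about r = 0.3 at s0 = 0.82 and r = 0.4 at s0 = 1.0. The largest loss is about 1.5 points, where the slope is near 1 and the covariate costs a degree of freedom without removing variance.

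**The case against.** The strongest reply is that the plan already uses baseline. Endpoint and sizing agree on a change score, which is valid under randomisation, and not stratifying on pain is no defect in a 40-patient trial. That stands as far as validity goes. It does not remove the dependence on imbalance in a single trial whenever the slope differs from 1.

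The list of model terms may also not be exhaustive, since the selection procedure refers to predictor variables in general. But baseline VAS is nowhere named as a candidate, and its retention would then turn on a p-value from the trial's own data.

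The calculation is also simpler than the planned analysis. It is a 12-month comparison in 16 completers per arm, whereas a longitudinal model can use partial data from up to 20. With 20 per arm the SEs of the baseline difference fall to 0.16, 0.26 and 0.32.

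Four stronger readings are tempting and should not be drawn.
- *The pain comparison is biased, or turns on baseline imbalance.* It is unbiased on average, and imbalance explains about 0% to 27% of its sampling variance under these assumptions, 3% in the middle case.
- *Adjustment would bring a large gain in power.* The usual formula with equal baseline and follow-up variances suggests 86% to 94% at correlations of 0.7 to 0.3. It implies baseline SDs of 2.14 to 1.40, above the 1.0 that scores of 5–7 allow. A wider spread is conceivable if the threshold is on another scale, or if baseline pain is retaken when "he/she will be rescheduled and that subsequent visit will serve as their initial study visit". The documents establish neither.
- *A treatment main effect averaged over visits including baseline would dilute the effect.* That would follow from leaving out a treatment-by-time term, not from leaving out baseline adjustment.
- *HOOS, WOMAC, PROMIS and the biomarkers would gain in the same way.* The documents give nothing from which to estimate this.

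**Conclusion.** The omission holds and should be corrected, though its likely size is modest. No section adjusts VAS for its baseline or constrains the arms to a common baseline mean. The consequence is conditional: some chance imbalance passes into this trial's estimate, with no systematic bias. The worst case considered, about 0.3 units for a 1-SE imbalance, needs baseline SD 1.0 and correlation 0.1 together; the middle case is about 0.1 unit. Power after adjustment runs from about 79% to 89% against 80%, so the argument does not rest on power. It rests on replacing an assumed slope of 1 with an estimated one and on fixing the primary contrast before the data are seen. All these figures depend on the back-solved SD of change and on assumed baseline SDs and correlations, so confidence in the size is only moderate.

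**What to change.** For VAS, prespecify one mixed model. The responses are the 6-week, 3-, 6- and 12-month scores. The fixed terms are baseline VAS, treatment, visit as a categorical factor and treatment-by-visit, with within-patient correlation modelled. An acceptable alternative keeps baseline as a response and constrains the arms to a common baseline mean. Name the visit whose VAS counts as baseline. Report the 12-month treatment contrast, to match the first-to-last-visit difference used for sizing. State that the treatment, visit and baseline terms are fixed and not subject to the p = 0.10 deletion. The same form may be used for the secondary outcomes, each with its own baseline, but this is optional.

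The cost is a few lines of text, with no new data or visits. The baseline term takes one degree of freedom and could lose up to about 1.5 points of power if the slope is near 1. Treatment-by-visit over four visits adds three parameters if the plan did not already intend it. A 12-month contrast is also less powerful than an average over visits if the effect is constant from 6 weeks, but that cost comes from the time point on which the trial was sized, not from the baseline term.

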# **Potential Pitfalls and Limitations:**

The study team has extensive experience studying FAI in patients in our MedSport clinic at the University of Michigan. All techniques and methodologies are currently in use and have previously been published in top orthopaedic journals. The main limitation we perceive is recruiting a sufficient number of subjects to the study. However, we have a high volume of patients pursuing treatment for FAI and anticipate it would be easy to recruit subjects into the study. While we think that a mixed-effects linear regression model is appropriate and informative for this study, an alternative approach would be a two-way repeat measures ANOVA. Given the statistical expertise of the study team, we do not anticipate any problems in performing analyses.

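### The Kellgren-Lawrence grade, an ordinal reading taken twice, is assigned to a linear mixed model whose confidence interval fails if few patients change grade

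*Combined protocol and SAP*

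**What the plan says.** The secondary outcome, under Plan for measurement of these outcomes, is "Change in Kellgren-Lawrence classification scores calculated from AP pelvis radiographs between pre-treatment and 1 year post-treatment". It carries the radiographic half of Hypothesis 2.

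Under Data Collection, "Hip radiographs will be performed at baseline and at 12 months", and films are "graded Stage 1-4 via Kellgren-Lawrence classification in a blinded fashion". The Inclusion Criteria require grade 2 or lower and the Exclusion Criteria remove grade 3 or higher. On the scale as stated, only stages 1 and 2 can occur at entry.

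Data Analysis says: "We will use a mixed-effects linear regression model to look at the changes in individual parameters at multiple time points". The terms follow: "Independent variables in the model are treatment assignment and time, dependent" "variables are outcomes scores, biomarkers and Kellgren-Lawrence scores". No treatment-by-time term is listed. Variables are then dropped stepwise at p=0.10, separately for each dependent variable, and the checks are model fitting and residual plots.

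Potential Pitfalls and Limitations adds only that "an alternative approach would be a two-way repeat measures ANOVA", which is also a linear method. No ordinal, rank or exact method is named for the grade.

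**The concern.** A grade confined to 1 or 2 at entry and read again a year later gives a change that will be zero for most patients and one for a few. A normal-theory standard error estimated from such data can be far too small, and it is exactly zero if nobody changes. The result would be an interval that looks precise when the data say little. Residual plots would show the poor fit, but the plan names no other analysis to turn to.

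The second difficulty is the estimand. The outcome is defined as a change between two readings. A model with only treatment and time as terms compares the arms on the average of the two readings, not on the change.

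At stake is the estimate for one secondary outcome. Whatever the trial finds on radiographic progression, a reader would want to know how large a difference the data could still hide.

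**Working it through.** **Inputs.** From Data Analysis: 32 evaluable patients, 16 per group, and 40 recruited. The dropout step reproduces: 32/(1 - 0.20) = 40. The 16 per group was set for pain and its standard deviation is not given, so it cannot be reproduced independently. No progression rate, effect size or power is stated for the grade. Assumptions: progression of 2-10% in a year, one-grade changes, no improvement, two-sided tests.

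**Interval.** With two balanced visits, the treatment-by-time estimate equals the difference in mean change. If a of 16 worsen in one arm and b of 16 in the other:

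- d = a/16 - b/16
- s² = (16/15) × p(1 - p) in each arm, with p = a/16 or b/16
- SE = √[(s²a + s²b)/16], and the interval is d ± 2.042 × SE (t, 30 df)

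Example, 4 v 0: d = 0.25, s² = 0.20 and 0, SE = √(0.20/16) = 0.112, interval 0.02 to 0.48, p = 0.033.

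**Coverage.** Each pair (a, b) is weighted by its binomial probability, and the weights are summed where the interval contains the true difference.

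- *5% v 0%.* With nobody changing, the interval is 0 to 0 and misses 0.05; the chance is 0.95^16 = 0.440. From 1 v 0 (-0.065 to 0.190) to 4 v 0 (0.022 to 0.478) it covers. At 5 v 0 the lower limit is 0.068 and it misses; 5 or more has probability 0.001. Coverage = 1 - 0.440 - 0.001 = **0.56**.
- *10% v 0%.* The no-change chance is 0.90^16 = 0.185. At 6 v 0 the lower limit is 0.375 - 2.042 × 0.125 = 0.120, a miss; 6 or more has probability 0.003. Coverage = 1 - 0.185 - 0.003 = **0.81**.
- *10% v 5%.* The no-change chance is 0.185 × 0.440 = 0.08. Lopsided splits, such as 0 v 2 (upper limit 0.049) and 5 v 0, add about 0.04. Coverage is **0.88**.
- *2% v 0%, the low end.* Coverage is at most 1 - 0.98^16 = 0.28.

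Most of the shortfall is the zero-width case. With all 40 patients retained, coverage is at most 1 - 0.95^20 = 0.64 for 5% v 0% and 1 - 0.90^20 = 0.88 for 10% v 0%. By the same enumeration at 16 per arm, 20% v 10% gives about 0.95, so the problem depends on progression being rare.

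**Chance that none of 32 changes, equal rates.** 0.98^32 = 0.52; 0.95^32 = 0.19; 0.90^32 = 0.03. For comparison, the exact 95% upper limit for 0 of 16 in one arm is 1 - 0.025^(1/16) = 0.21. The linear interval would be 0 to 0.

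**Model as literally listed.** Constructed data at 16 per arm, with stages 1 and 2 balanced at baseline and 4 v 0 progressions: the treatment-by-time estimate is 0.25, the true difference in change. With treatment and time only, the treatment coefficient is 0.125 (p = 0.51), half that difference, because it averages a baseline without any difference with the 12-month reading. Across 3 v 0 and 4 v 0, at 16 or 20 per arm, its p-value was 0.50 to 0.65.

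**The case against.** The strongest reply is that the linear test is not too liberal. Under equal true rates and 16 per arm, it rejects at nominal 0.05 with probability 0.0003, 0.006 and 0.028 at 2%, 5% and 10% progression. Over rates up to 30%, at 16 or 20 per arm, the largest values are 0.053 at 0.05 and 0.106 at 0.10. A normal instead of a t reference gives at most 0.058 and 0.121, at the higher rates. It follows that coverage is above nominal when the arms do not differ (1 - 0.006 = 0.994 at 5%). This stands: undercoverage arises only when the arms truly differ.

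A reader might set 4 v 0 at p = 0.033 (linear) against p = 0.101 (Fisher), or 3 v 0 at 0.073 against 0.226, and infer that the plan would produce false claims. The figures are right but the inference is not. Fisher is very conservative here: its actual size at nominal 0.05 is 0.0008 at 5% progression. For 4 v 0 Barnard gives 0.045 and Boschloo 0.050, close to the linear result. The 3 v 0 split passes only the 0.10 stepwise threshold. With one progression in the other arm, the linear p-value is 0.30 (3 v 1) or 0.15 (4 v 1). All these linear p-values also need a treatment-by-time term that the plan does not list.

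Three further points are fair. The low rate is an assumption. The plan does not say that it will report confidence intervals, so the interval judged here is the one its model would yield. And if nobody changes, an exact test is uninformative too; only the exact interval says something useful.

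**Conclusion.** The concern holds as a weakness of estimation. If about 2-10% of patients change grade in a year, the model's 95% interval for the difference in change covers well below 95% when the arms differ: about 56% at 5% v 0%, 81% at 10% v 0% and 88% at 10% v 5%, with 16 per arm. With no changes it collapses to zero width. In addition, the terms as listed do not estimate the change that the outcome section defines. The aim of modelling changes may imply a treatment-by-time term, but none is written.

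The documents do not support the stronger reading, that this analysis biases the trial towards false radiographic findings. They also give no rate that would confirm progression is rare. The point is minor: it touches one secondary outcome that does not enter the sample size.

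**What to change.** In Data Analysis, remove the Kellgren-Lawrence grade from the mixed-model and stepwise list. In its place:

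- tabulate change in grade from baseline to 12 months per arm (improved, unchanged, worsened);
- report the number per arm worsening by one grade or more, with an exact confidence interval for the difference;
- compare the arms with an exact test, preferably unconditional (Barnard or Boschloo), named in advance, because Fisher is very conservative at these counts.

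This takes a sentence or two and uses data already collected. The cost is a wider interval, some loss of power, and loss of the size of change in the comparison; the table keeps improvements visible. An ordinal or rank analysis of change would also be defensible, but would still need an exact or permutation method with so few changes. The primary pain analysis needs no alteration on this account.

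### The p=0.10 stepwise rule can delete the randomised treatment term, including for the primary VAS, and the level for the treatment test is not stated

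*Combined protocol and SAP*

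**What the plan says.** The Data Analysis section is the only statistical plan. Its steps are:

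- **Sample size.** The trial is powered at 80% with alpha 0.05 for a "difference in the change in pain between the first and last visit of 1.7 units", giving 32 patients (16 per arm), raised to 40 for 20% withdrawal.
- **Model.** A mixed-effects linear regression will examine changes over time and associations between changes in several parameters. "Independent variables in the model are treatment assignment and time"; no other covariate and no treatment-by-time term is named. The dependent variables are outcome scores, biomarkers and Kellgren-Lawrence scores.
- **Selection.** Univariable models come first, to "explore the relative importance of each predictor variable followed by a stepwise procedure". Significant variables enter a multivariable model, which is then reduced by "dropping the highest non-significant variable (significance will be set at p=0.10) until only significant variables remain".
- **Scope.** "This will be repeated for each dependent variable".

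The section on measuring outcomes defines the primary outcome as change in the 7-point pain VAS, so the primary outcome is one of those dependent variables. The Potential Pitfalls section mentions repeated-measures ANOVA, but only as an alternative approach.

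**The concern.** In a randomised trial the treatment contrast is the result, and it should be estimated and reported whatever its p-value. Here treatment is one of only two named candidates for deletion. Three consequences follow.

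1. **Selective reporting.** If the final model is what gets reported, a null or modest result leaves no treatment estimate or confidence interval in it, and the estimates that survive are too large on average.
2. **Wrong quantity under test.** The trial is powered for a between-group difference in first-to-last-visit change, which is a treatment-by-time contrast. Main effects of treatment and time do not contain it. Treatment can therefore be dropped while the powered contrast is present.
3. **Unclear alpha.** The sample size uses 0.05, but the only level in the analysis procedure is 0.10. The plan does not say whether 0.10 is solely a retention threshold. If retention is read as significance, the type I error is 10%, not the planned 5%.

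**Working it through.** **Inputs from the plan:** difference 1.7, power 80%, alpha 0.05, 16 evaluable per arm, 20 per arm recruited, visits at 0, 1.5 (6 weeks), 3, 6 and 12 months.

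**Assumptions, because the plan is silent:** a two-sided test; equal within-patient correlation ρ of 0.3, 0.5 or 0.7; equal SD at every visit; complete data; true 12-month difference 1.7 unless stated.

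**Step 1: the plan's own figure.** N=32 cannot be reproduced independently, since no SD is given. Solving two-sample t-test power = 0.80 at 1.7 with n=16 and alpha 0.05 gives an SD of change of 1.66 (1.89 if one-sided). The withdrawal step reproduces: 32/(1−0.20) = 40.

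**Step 2: simple change-score comparison (not the planned model, but the one powered).** Treatment is dropped when p≥0.10. The drop probability is 1 − power at two-sided 0.10, from the noncentral t with 2n−2 df and noncentrality δ/(SD·√(2/n)). For δ=1.7 and n=16 the noncentrality is 1.7/(1.66×0.354) = 2.90. Retained means come from 1,000,000 simulated trials per case.

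| True δ | n per arm | Dropped | Mean estimate if retained | Inflation |
|---|---|---|---|---|
| 1.7 | 16 | 12% | 1.83 | 8% |
| 0.85 | 16 | 59% | 1.39 | 63% |
| 1.7 | 20 | 6% | 1.77 | 4% |
| 0.85 | 20 | 52% | 1.28 | 50% |

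With no true effect, treatment is dropped in 90% of trials and the signed bias is zero. With SD 1.89 and 16 per arm, the drop rates are 20% and 65%.

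**Step 3: the model as listed (random intercept, treatment and time main effects, VAS at five visits).** With balanced data the treatment test compares patients' five-visit means.

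- SD per visit = 1.66/√(2(1−ρ)) = 1.40, 1.66, 2.14.
- SD of a five-visit mean = SD per visit × √((1+4ρ)/5) = 0.93, 1.29, 1.87.
- Average effect over visits: constant from 6 weeks, 1.7×4/5 = 1.36; linear growth to 12 months, 1.7×(0+1.5+3+6+12)/(5×12) = 0.64.

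| Effect shape | n per arm | ρ=0.3 | ρ=0.5 | ρ=0.7 |
|---|---|---|---|---|
| Constant | 16 | 1% | 10% | 36% |
| Linear | 16 | 40% | 61% | 75% |
| Constant | 20 | 0.2% | 5% | 27% |
| Linear | 20 | 31% | 54% | 72% |

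The entries are the probabilities that treatment is dropped. If the univariable entry level is 0.05 and not 0.10, the range with 16 per arm is 2% to 85%. Simulation with 16 per arm shows treatment dropped while the first-to-last contrast has p<0.05 in 0.6% (constant, ρ=0.3) to about 60% (linear, ρ=0.7) of trials.

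**Step 4: what the alpha choice does.** At SD 1.66 and 16 per arm, power is 80% at two-sided 0.05 and 88% at 0.10; at 0.10, 13 per arm would give 80%. The two levels are not interchangeable.

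**The case against.** - **0.10 is only a retention threshold.** This is the more natural reading, because the level sits inside the deletion clause and 0.05 appears in the same section. Dropping treatment at p≥0.10 does not by itself raise type I error. What stands is that the plan never gives the level for the treatment test.
- **The selection was meant for the association models.** Stepwise selection over two design variables serves little purpose, and association models would need more predictors. But those predictors are not named, nothing limits the procedure to such models, and it is to be repeated for every dependent variable.
- **The comparison is not lost.** The univariable step fits treatment alone, and with complete balanced visits and no interaction that estimate equals the one adjusted for time. This is correct, but the step's stated purpose is exploratory and nothing makes it the reported test. The harm depends on the final model being what is reported.
- **Two defects are merged.** The largest drop rates arise mainly because the listed model averages over visits. Forcing in only a treatment main effect would not recover the powered contrast. This is right, and it is why the remedy needs the interaction. The change-score figures isolate the selection rule.
- **The assumed SDs are too large.** If the entry criterion of VAS 5 or more refers to the 7-point scale, baseline SD is at most about 1. Setting it at 0.5 to 1.0 (baseline correlation 0.2 to 0.4, follow-up correlation 0.3 to 0.7) gives drop rates with 16 per arm of about 1% to 13% (constant) and 40% to 63% (linear). This lowers the top of the range.
- **The outcome is change from baseline.** Modelling change at the four follow-ups avoids diluting a constant effect. Under the equal-SD assumption, the SD of a patient's mean change is 1.66×√0.625 = 1.31, whatever ρ. The average effect is 1.7 (constant) or 1.7×22.5/(4×12) = 0.80 (linear). With 16 per arm, treatment is then dropped in about 3% and 49% of trials. The problem is smaller for a constant effect and remains for a growing one.

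**Conclusion.** The concern holds. Followed as written, the rule can delete the randomised comparison for every outcome, the primary VAS included, and the plan does not say which treatment estimate is to be tested or reported. This rests on the wording, not on any one scenario.

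The size is illustrative. Selection alone, in the powered change-score comparison with 16 per arm, removes treatment in 12% of trials at the design effect and 59% at half of it, with survivors inflated by 8% and 63%. In the main-effects model the loss at the design effect is 1% to 75%, depending chiefly on whether the effect is constant or grows; the upper end needs ρ=0.7 and a baseline spread that may be too wide. The 10% type I error applies only if 0.10 is also the level for inference. Because the defect reaches the primary analysis, it should be corrected before the data are analysed.

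**What to change.** Amend the Data Analysis section to state that:

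1. No variable selection applies to any treatment comparison. Treatment, visit and treatment-by-visit stay in every model.
2. The primary test is the treatment difference in VAS change from the first to the last visit, the contrast used for the sample size, at two-sided 0.05.
3. The treatment estimate and 95% CI are reported for every outcome, whatever the p-value.
4. Stepwise selection at 0.10 is limited to models of associations between parameters, labelled exploratory, with 0.10 described as a retention threshold only.

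Stating only that treatment and time are retained would stop the deletion but would leave the powered contrast outside the model.

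The cost is wording. Sample size is unaffected: 16 per arm keeps 80% power at the back-solved SD, and the total of 40 stands. If the team had intended 0.10 for inference, fewer results could be called significant.
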